A feasibility study addressing the frequency of Low Level Laser Therapy for reducing central adiposity and weight in overweight individuals.

NCT02877004

10/28/16

Currently in the United States about 97 million adults are overweight, accounting for about 33% of the American adult population¹. Low level laser therapy (*LLLT*) is a new novel non-invasive procedure that removes excess fat without the negative side effects associated with surgical methods. *LLLT* also has the potential to enhance motivation for weight management as *LLLT* treatment can provide immediate feedback to the patient or study participant in the form of lost inches which can be seen by the individual. *LLLT* has been associated with reductions in waist circumference of 6-12 inches with 6 treatments.

Clinically, the *LLLT* treatments can vary from 6 to 28 treatments and a frequency of 1-3 times per week depending on the patients' preference and ability to pay. Our research team conducted a previous feasibility study of 45 overweight/obese subjects looking at the use of 12 *LLLT* treatments over the course of 12 weeks (one treatment per week) with the end goal of reducing central adiposity. In this prior study (IRB 14-002370), subjects were randomized to 1 of 3 conditions (*LLLT*, lorcaserin, and *LLLT* + lorcaserin). This study demonstrated feasibility by recruiting the goal of 45 obese subjects within 3 months. The subjects assigned to *LLLT* did not have any adverse events reported during the 6 months of the trial and although the sample size was too small for any significant findings, the *LLLT* did show a reduction in body circumference (2.3 to 4.0 cm reduction) and a reduction in weight (1 to 3.5 kg reduction). At this point, the question still remains on the ideal frequency of *LLLT* treatments which are needed to see a significant loss in weight and reduction in body circumference. Significant weight loss is defined as a reduction of 5% or more of the baseline weight.

For the purposes of this study we will define overweight as having a body mass index [BMI] 25-29.9. In this pilot study we will randomize 60 overweight individuals to one of three *LLLT* treatment schedules:

1. 12 treatments of *LLLT* - 3 times per week
2. 12 treatments of *LLLT* - 2 times per week
3. 12 treatments of *LLLT* - 1 time per week

The overarching purpose of this study is to obtain preliminary evidence regarding the most efficacious frequency of *LLLT* treatments to obtain at least a 5% weight loss and to produce reduction in body circumference.

Hypothesis: We hypothesize that an increase frequency of *LLLT* treatments will produce a greater weight loss and greater reduction in body circumference when compared to a less frequent schedule of *LLLT*:

Group 1 weight loss > Group 2 weight loss > Group 3 weight loss

Group 1 reduction in body circumference > Group 2 reduction in body circumference > Group 3 reduction in body circumference

Aims, purpose, or objectives:

1. To compare the % of weight loss and reduction in body circumference at the end of 4 weeks for overweight individuals undergoing *LLLT* treatments at different frequencies

Study Design and Methods

Methods:

Study Design - This will be an open label clinical trial with all study participants receiving *LLLT*. We will obtain preliminary data on the efficacy of *LLLT* based on varying frequency of the *LLLT* treatments. We will focus this study on 60 overweight adults with a BMI of 25 to 29.9. We will assess changes in weight and waist circumference at end of treatment for group 1 (week 4) and group 2 (week 6) and group 3 (week 12). Participants will be randomized to receive *LLLT* treatments either 3 times a week for a duration of 4 weeks (group 1); 2 times a week for a duration of 6 weeks (group 2); or once a week for a duration of 12 weeks (group 3).

Study Procedures: We will use standardized procedures to ensure that uniform instructions are provided to all participants and that recruitment and screening result in the enrollment of appropriate study participants. All Study Case Report Forms are paper documents and also function as study source documents. The data will be entered into an online electronic data program (Redcap) by research staff within 7 days of the completed study visit. Study participant data on this system will be identified using unique subject IDs, not personal identifiers. This data entry system will provide immediate feedback on the majority of data integrity issues, including implausible entries, and checks of consistency between variables.

Study Processes and Procedures

Intervention

LLLT: Each *LLLT* device consists of a multiple-head low-level diode laser with 6 independent diode laser heads (**Figure 2**). Each diode emits 532 nm (green) laser light. In the active device (Erchonia1 LipoLaser, Erchonia Medical, Inc., McKinney, TX)² each diode generates a 17 mW output. The average number of treatments can vary, depending on the adipose make up on the patient.³ In this trial, *subjects will undergo 12 treatments of LLLT at varying frequencies*.

The *Erchonia® Zerona™ 2.0 Laser* (which will be used in this study) has been approved by the FDA (K123237) as a non-invasive dermatological aesthetic treatment which can be used by individuals intending to reduce circumference of hips, waist, and thighs. Justification for the assertion of anticipated safety and effectiveness of the *Erchonia® Zerona 6 Headed Scanner (EZ6)* for application to reducing body circumference is found through several FDA clearances for *Erchonia® Low Level Laser* devices for body circumference reduction indications. For all of the 510(k) clearances, the assigned Product Code is OLI, defined as follows:

- ✓ Device: Fat reducing low level laser
- ✓ Regulation Description: Low level laser system for aesthetic use
- ✓ Definition: Non-invasive reduction in fat layer for body contouring
- ✓ Technical Method: Use of low level laser energy to create pores in adipocyte cells to release lipids (triglycerides)
- ✓ Target Area: Adipocyte cells within the subcutaneous fat layer of the body, this could include abdomen (waist), thighs and hips

Figure 2. LLLT device - Zerona® by Erchonia

Under 21 CFR 878,5400, the FDA identifies this generic type of device as: “A Low Level Laser System for Aesthetic Use is a device using low level laser energy for the disruption of adipocyte cells within the fat layer for the release of fat and lipids from these cells for non-invasive aesthetic use.”

The procedure administration protocol for each session is as follows:

- The study participant is correctly fitted with the safety glasses.
- The participant lies comfortably flat on his or her back on the procedure table such that the front area of the subject’s body is facing upwards.
- The Erchonia® Zerona 6 Headed Scanner (EZ6) diodes are positioned at a distance of 6 inches above the subject’s lower and upper abdomen, stomach, centered along the body’s midline (the “line” that vertically “dissects” the body into two equal halves).
- The Erchonia® Zerona 6 Headed Scanner (EZ6) is then activated for 30 minutes over the subject’s anterior (frontal) region. Each scanner emits to the subject a laser beam of approximately 17 mW with a wavelength of 532 nm, and creates a spiraling circle pattern that is totally random and independent from the others. These patterns overlap each other to guarantee total coverage within the target area of approximately 80 in²/516 cm².
- The participant then turns over to lie flat on his or her stomach such that the posterior treatment area of the subject’s body encompassing the region spanning from the participant’s back down through the central body region is facing upwards.
- The Erchonia® Zerona 6 Headed Scanner (EZ6) diodes are positioned at a distance of 6 inches above the posterior treatment area, centered along the body’s midline, the same as for the anterior region.
- The Erchonia® Zerona 6 Headed Scanner (EZ6) is then activated for 30 minutes over the subject’s posterior region. Each scanner emits to the subject a laser beam of approximately 17 mW with a wavelength of 532 nm, and creates a spiraling circle pattern that is totally random and independent from the others. These patterns overlap each other to guarantee total coverage within the target area of approximately 80 in²/516 cm².
- The participant’s safety glasses are removed and the procedure administration session is over.

The Erchonia expert trained the DOM CRO staff in-person on the use and maintenance of the LLLT on December 12, 2013 for a prior study utilizing LLLT. This training session has been documented. They will be available for on the spot questions and for any online retraining, as needed. The study coordinators will be under the direction of the nurse coordinator/supervisor ([name]).

Subject Information

Target accrual: We plan to enroll and screen a maximum of 75 overweight individuals with a BMI of 25-29.9 kg/ m² in order to accrue 60 research participants.

Subject population: Participants will be recruited from the local community through radio, internet postings, Mayo Clinic physician referrals.

Based upon our recruitment data from recent weight loss studies and a wait list of participants who are interested in this treatment, we estimate recruiting 3-4 study participants per week. Those who meet study criteria will be invited to participate in this open label study. In this study, all 60 study participants will receive

LLLT treatments. Everyone will be in the study for 6 months, but will be in treatment for varying periods of time based on the randomization group they will be assigned:

1. 12 treatments of LLLT 3 times per week (M W F) for a duration of 4 weeks
2. 12 treatments of LLLT 2 times per week (T Th) for a duration of 6 weeks
3. 12 treatments of LLLT 1 time per week for a duration of 12 weeks

Inclusion Criteria: Potentially eligible subjects must:

1. be over 18 years of age;
2. have a body weight of greater than 50 kg (110 pounds);
3. have a BMI 25–29.9 kg/m²;
4. be able to participate fully in all aspects of the study; and
5. have understood and signed study informed consent.

Exclusion Criteria: Subjects will be excluded if they:

1. have used weight loss medications or participated in a weight loss program within the past 30 days;
2. are currently taking supplements known to affect weight, such as *garcinia cambogia*;
3. have had weight fluctuations of 20 pounds or more in the past 6 months (self-report);
4. have an implanted device (including pacemaker or lap band) in the targeted area of LLLT;
5. have a known active eating disorder;
6. have a known, active, untreated clinically significant psychiatric condition (alcohol or substance abuse, psychosis, bipolar disorder, or depression);
7. have used an investigational drug within 30 days of study enrollment;
8. are currently pregnant or lactating, or are of child-bearing potential or are likely to become pregnant during the medication phase and are unwilling to use a reliable form of contraception; Acceptable forms include:
 - a. Hormonal methods, such as birth control pills, patches, injections, vaginal ring, or implants
 - b. Barrier methods (such as a condom or diaphragm) used with a spermicide (a foam, cream, or gel that kills sperm)
 - c. Intrauterine device (IUD)
 - d. Total hysterectomy or tubal ligation
 - e. Abstinence (no sex)
9. have a history of any major cardiovascular events including heart valve disease, cardiac arrhythmias, congestive heart failure, acute coronary syndrome, stroke, transient ischemic attack, or peripheral vascular disease;
10. have current uncontrolled hypertension (systolic > 160 mm Hg or diastolic > 95 mm Hg) documented on 2 separate occasions;
11. have clinically significant acute or chronic progressive or unstable neurologic, hepatic, renal, cardiovascular, lymphatic, respiratory, or metabolic disease (such as diabetes) or active cancer or are within 1 year of cancer remission;
12. surgical intervention for body sculpting/weight loss, such as liposuction, abdominoplasty, stomach stapling, lap band surgery, etc. within 12 months prior to enrollment.
13. medical, physical, or other contraindications for body sculpting/weight loss;
14. any medical condition known to affect weight levels and/or to cause bloating or swelling;
15. a diagnosis of, and/or taking medication for, irritable bowel syndrome;
16. active infection, wound or other external trauma to the areas to be treated with the laser;
17. known photosensitivity disorder;

18. current active cancer or currently receiving treatment for cancer; or
19. have a known history of any condition or factor judged by the investigator to preclude participation in the study or which might hinder adherence

Will a Certificate of Confidentiality be obtained? No.

Research Activity

1. **Drug & Device:** Drugs for which an investigational new drug application is not required. Device for which (i) an investigational device exemption application is not required; or the medical device is cleared/approved for marketing and being used in accordance with its cleared/approved labeling. (Specify in the Methods section)
2. **Survey, Interview, Focus Group:** Research on individual or group characteristics or behavior, survey, interview, oral history, focus group, program evaluation, etc. (Specify in the Methods section)

Data Analysis

Statistical Considerations

The primary aim of this study is to assess the feasibility and potential efficacy of using LLLT at varying frequencies to reduce central adiposity in overweight individuals.

The purpose of a phase II trial is to decide whether additional studies of the experimental regimen are warranted and to provide preliminary data for designing a larger phase III trial to confirm efficacy. Although there has been debate about the value of formal statistical comparisons in phase II trials, we agree with those who propose that formal comparisons are appropriate under the caveat that phase II studies are not expected to provide reliable definitive comparisons using a traditional two-sided type I error rate of 0.05.(references). For a randomized phase II trial, a one-sided test with a false-positive (type I error) rate of 0.20 is considered appropriate for the primary comparison to assess whether additional studies of the given regimen are warranted.

For the current study the primary endpoint is change in waist circumference (WC) from baseline. For the primary analysis, the change in WC from baseline to week 4 will be compared across frequency groups.

Data Analysis Plan:

Data related to subject recruitment will be summarized, including the frequency of calls and the reasons for failing screening criteria.

Baseline characteristics and treatment compliance of the enrolled participants will be presented overall and also separately for each of the treatment groups. In all cases, data will be summarized using mean \pm SD for continuous variables and frequency percentages for nominal variables. Treatment adherence will be quantified for each individual by calculating the percentage of treatment sessions attended and the percentage of medication used. The percentage of subjects who discontinue study participation and the reasons for discontinuing study participation will be summarized. Changes in measures of central adiposity and weight from baseline will be summarized at each study visit. The primary outcome of interest is change in waist circumference from baseline to week 4. For the primary comparison, the group receiving one LLLT session per

week will be the control group and the groups receiving two and three sessions per week will be considered the experimental groups. The mean change from baseline WC for each of the experimental groups will be compared to control using the two-sample t-test. For these comparisons, a one-tailed p-value of 0.20 or less will be considered evidence suggesting that studies utilizing increased frequency of LLLT sessions are warranted.

Sample-size justification:

The primary endpoint for the current investigation is change in WC from baseline to week 4. The group having one LLLT session per week will be considered the control group. From our previous study, the mean \pm SD change in WC from baseline in those receiving 1 LLLT session per week was -1.1 ± 1.9 cm. In order to be considered meaningful, we would expect an increased frequency of LLLT sessions to result an additional reduction of approximately 1.0 cm. Under the assumption that the SD is 1.9cm, a sample-size of N=20 per group will provided statistical power (one-tailed, alpha=0.20) of approximately 80% to conclude that additional studies are warranted (i.e. detect a difference between groups of 1.0 cm). Therefore, a sample-size of N=20 per groups will be used for the present study.

References

2. Erchonia Corporation. Zerona. [Web Page]. 2011; <http://www.myzerona.com/professional>. Accessed 01 Sept 2011.

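### In an open-label trial with a directional hypothesis, nothing described shields the waist circumference reading from knowledge of group or earlier values, and the decision threshold is only 0.51 cm

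*Combined protocol and SAP*

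**What the plan says.** - **Masking.** Under Study Design: "This will be an open label clinical trial with all study participants receiving" LLLT. Subject Information repeats that the study is open label.
- **Expected direction.** The Hypothesis paragraph predicts that three sessions a week will reduce body circumference more than two, and two more than one.
- **Endpoint.** Data Analysis Plan: "The primary outcome of interest is change in waist circumference from baseline to week 4".
- **Test and decision rule.** The mean change in each of the two more frequent groups "will be compared to control using the two-sample t-test", with the once-weekly group as control. Then "a one-tailed p-value of 0.20 or less will be considered evidence suggesting that studies utilizing increased frequency of LLLT sessions are warranted". Meeting this rule is called a *go* below.
- **Planning values.** Sample-size justification: "Under the assumption that the SD is 1.9cm", 20 per group gives about 80% power to "detect a difference between groups of 1.0 cm".
- **Staff.** Intervention section: "The study coordinators will be under the direction of the nurse coordinator/supervisor". The number of coordinators and their rota are not given.
- **Measurement.** Nothing states who reads WC, with what instrument, at what body site or how many times. Nothing states whether the reader knows the group or the earlier value, or whether baseline is recorded before allocation is known. The standardised procedures under Study Procedures concern participant instructions, recruitment and screening. The laser session, by contrast, is specified down to the distance of the diodes and the minutes per side.

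**The concern.** A circumference reading leaves some room for judgement. A reader who knows the schedule, the earlier value and the hypothesis may, without intending to, record slightly larger reductions in the groups expected to do better. Because the hypothesis is directional and both comparisons use the once-weekly group as control, such an effect would favour a go in both.

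The plan is sensitive to small shifts because its decision rule is deliberately lenient. A one-tailed level of 0.20 is a defensible choice for a study of this kind, but it budgets only for chance error. A systematic difference in reading between groups adds to that 20% unseen, and no later analysis can separate it from a treatment effect. The data-entry checks look for implausible values and inconsistencies between variables, and a shift of a few millimetres is neither. At stake is the one decision the trial is built to inform: whether more frequent schedules deserve further study.

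**Working it through.** **Inputs.** SD of change 1.9 cm, n = 20 per group and target difference 1.0 cm (Sample-size justification); one-tailed 0.20 and a two-sample t-test against the once-weekly group (Data Analysis Plan). The bias sizes are assumptions.

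**1. Reproduce the plan's power.**
- Standard error of a difference = 1.9 × √(2/20) = 0.601 cm, with 38 degrees of freedom.
- Power at 1.0 cm is 79.2% by the noncentral t and 79.5% by the normal approximation. The stated figure of about 80% is confirmed.

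**2. Smallest observed difference that gives a go.**
- t(0.80; 38 df) × SE = 0.851 × 0.601 = 0.51 cm, if the observed SD equals 1.9 cm. This is about half the 1.0 cm that the plan treats as meaningful.

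**3. Chance of a go with no true effect and a reading bias b.** Here b is the extra reduction recorded in an experimental group minus that recorded in the control group. An error of the same size in every group gives b = 0. The chance is the upper tail of a noncentral t with 38 df and noncentrality b / 0.601, beyond 0.851.

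| b (cm, assumed) | b / 0.601 | Go, per comparison | At least one go, same b in both experimental groups |
|---|---|---|---|
| 0 | 0 | 20% | 31% |
| 0.1 | 0.17 | 25% | not computed |
| 0.25 | 0.42 | 33% | 49% |
| 0.5 | 0.83 | 49% | 66% |

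The last column comes from 400,000 simulated trials with a shared control group.

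**4. Sensitivity to the SD.** The 1.9 cm is itself a planning value.

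| SD (cm) | Go threshold (cm) | Go per comparison at b = 0.5 cm |
|---|---|---|
| 1.5 | 0.40 | 58% |
| 1.9 | 0.51 | 49% |
| 2.5 | 0.67 | 42% |

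**5. Would repeat readings help?** If single readings have independent error with SD e, the variance of a change contains 2e². Averaging two readings at each visit halves that to e², so the SD becomes √(1.9² − e²).
- e = 0.5 cm: √(3.61 − 0.25) = 1.83 cm, power about 81%.
- e = 1.0 cm: √(3.61 − 1.00) = 1.62 cm, power about 87%.

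Both values of e are assumptions, and the gain also requires that the earlier study's 1.9 cm came from single readings, which the document does not say. Averaging does nothing about a directional bias. At SD 1.62 cm the threshold falls to 0.851 × 1.62 × √0.1 = 0.44 cm, and a bias of 0.5 cm gives a go about 55% of the time instead of 49%.

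**The case against.** The strongest reply has four parts.

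- **Open label is a declared and largely unavoidable choice.** Participants and treating staff cannot be masked to visit frequency. That stands, but it does not extend to the reading. Recording baseline before allocation and withholding earlier values need no masked person.
- **The bias is hypothetical, and 0.5 cm sits almost on the threshold.** In any trial, a bias equal to the critical difference gives about an even chance of success. This stands as a caution: 0.5 cm is an illustration and should not be read as an expected bias. All groups receive active LLLT, so only a difference in expectation between schedules matters, and it could be small. At 0.1 cm the rate moves only from 20% to 25%.
- **This is a feasibility study.** Statistical Considerations disclaims definitive comparisons, and a go means only that more work is warranted. That limits the harm but does not remove it, since that decision is the trial's main product.
- **Masking may fail.** Groups 1 and 2 have fixed treatment days (M W F and T Th), so the day of a reading can reveal the group, as can the participant. In a small team it may be hard to find a coordinator who has delivered none of a participant's sessions. Both limits stand, and they are why the third part of the fix is conditional.

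A reader might infer more: that WC is known to be read by tape without masking, or that a 0.5 cm bias would produce a go by itself. The document supports neither. It names no instrument and is silent on masking of the reading, which is not the same as ruling it out. A bias of 0.5 cm gives a go in about 49% of comparisons, against the 20% that the plan already accepts.

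**Conclusion.** The point holds as a low-cost improvement to the design. As written, the plan lets a reader who knows the group and the earlier values measure the endpoint that decides the trial, under a rule met by an observed difference of 0.51 cm. With no true effect, differential biases of 0.1, 0.25 and 0.5 cm would raise the false-go rate per comparison from 20% to about 25%, 33% and 49%.

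These figures rest on the plan's SD of 1.9 cm, 20 evaluable participants per group, approximately normal changes, and bias sizes that are assumed. They show how sensitive the decision is. They are not evidence that bias will occur, or of its size.

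**What to change.** Add to Study Procedures:

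1. Baseline WC is measured and recorded before the participant's allocation is opened.
2. The week-4 WC form does not show earlier values, and the reader does not look them up.
3. Where the existing coordinator rota allows, the week-4 reading is taken by a coordinator who has not delivered that participant's sessions and is not told the group.

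Repeat readings at a marked site may be added for precision only. They should not be presented as protection against bias, and any gain in power depends on the assumptions in step 5 of the working.

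**Cost.** One paragraph of procedure, a change to a paper case report form and some rota planning. Groups, endpoint, test and sample size are unchanged. The protection is partial, because participants or the fixed treatment days may reveal the group.

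### Does the plan leave its primary week-4 test without a waist reading in the twice-weekly and once-weekly groups?

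*Combined protocol and SAP*

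**What the plan says.** The Study Design paragraph, under Study Design and Methods, says that changes in weight and waist circumference will be assessed "at end of treatment for group 1 (week 4) and group 2 (week 6) and group 3 (week 12"). Each group has 12 sessions, given three times, twice or once a week.

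Four other statements use week 4:

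- The single numbered aim compares percentage weight loss and "reduction in body circumference at the end of 4 weeks for overweight individuals" treated at the different frequencies.
- Statistical Considerations says that "the change in WC from baseline to week 4 will be compared across frequency groups".
- The Data Analysis Plan says: "The primary outcome of interest is change in waist circumference from baseline to week 4".
- Sample-size justification says: "The primary endpoint for the current investigation is change in WC from baseline to week 4". It adds: "The group having one LLLT session per week will be considered the control group".

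The Data Analysis Plan also says: "Changes in measures of central adiposity and weight from baseline will be summarized at each study visit". The supplied text does not list those visits or give their weeks.

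**The concern.** The design sentence and the primary endpoint name different weeks for two of the three groups. If the design sentence were the measurement schedule, group 2 would be measured at week 6 and group 3 at week 12, and neither would have the week-4 value that the primary analysis needs. Group 3 is the control in both primary t-tests, so neither test could be run as specified. A waist measurement not taken on time cannot be recovered.

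The two timings also answer different questions. Week 4 compares unequal numbers of sessions on a common date. End of treatment compares equal numbers of sessions on unequal dates. In an open-label trial one would not want that choice left open until the results are known.

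The account of a treatment session seems to add to the worry. It is introduced by "The procedure administration protocol for each session is as follows" and contains no step for measuring waist or weight, so attending a session in week 4 does not by itself produce a reading.

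**Working it through.** **1. The plan's own figure.** Inputs from Sample-size justification: difference 1.0 cm, SD 1.9 cm, 20 per group, one-tailed alpha 0.20.

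- Standard error of the difference: 1.9 × √(2/20) = 0.601 cm.
- Standardised difference: 1.0 / 0.601 = 1.664.
- Normal approximation: Φ(1.664 − 0.842) = Φ(0.823) = 79.5%.
- Noncentral t with 38 degrees of freedom: 79.2%.

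The stated value of approximately 80% reproduces. It is the power of a comparison of week-4 changes with 20 readings per group.

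**2. Sessions received and timing.** Frequencies and durations come from Study Design and Subject Information. Sessions by week 4 are the weekly frequency × 4, counted after that week's last session.

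| Group | Sessions by week 4 | Sessions at end of treatment | Design-sentence week minus week 4 |
|---|---|---|---|
| 1 (three a week) | 3 × 4 = 12 of 12 (100%) | 3 × 4 = 12 | 4 − 4 = 0 weeks |
| 2 (twice a week) | 2 × 4 = 8 of 12 (67%) | 2 × 6 = 12 | 6 − 4 = 2 weeks |
| 3 (once a week) | 1 × 4 = 4 of 12 (33%) | 1 × 12 = 12 | 12 − 4 = 8 weeks |

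The timings therefore do differ for groups 2 and 3.

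**3. Whether the statements exclude one another.**

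- The design sentence says when an assessment takes place. It does not say that there is no other. End-of-treatment readings at weeks 4, 6 and 12 can stand beside a common reading at week 4, and in group 1 the two coincide.
- The primary endpoint is a waist change to week 4. The Data Analysis Plan names the once-weekly group as control and the other two as experimental. That fixes the measurement, the week and all three groups, so the reading is a necessary input to the stated analysis.
- Summaries at every study visit presuppose more readings than one at the end of treatment.
- Groups 2 and 3 are in treatment until weeks 6 and 12, so both attend in week 4 and no extra visit is needed.

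**4. What the session list can show.** It runs from fitting the safety glasses to taking them off and describes how the laser is applied. It also omits the baseline and end-of-treatment measurements, which the plan plainly intends. Its silence about week 4 is therefore no evidence that the week-4 reading is left out.

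**5. What writing it down would change.** It would call for at most 2 × 20 = 40 waist and 40 weight readings at sessions already attended, and none if they are already intended. The 20 per group, the t-tests, the alpha and the power in step 1 stay the same.

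**The case for a change.** The best case for a change is operational. The Study Design sentence is the one place that sets out assessment weeks group by group, and staff might well build a visit calendar from it. The week-4 statements sit in the aim and the statistical sections, which coordinators may not consult when booking measurements. The reference to study visits points to a list that the supplied text does not contain, and the six months of participation come without visit weeks either. The sentence describing the t-test names no week itself and takes it from its neighbours. Against an unrecoverable loss of the control reading, one added sentence costs almost nothing.

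Part of this stands. The design sentence is incomplete, and the supplied text has no visit list. It also does not say whether a week-4 reading comes before or after that week's session. In group 3 that decides whether 3 or 4 sessions precede it.

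The step from there to a defect does not stand. The loss occurs only if someone schedules measurements from one sentence and disregards the aim, the primary endpoint and the sample-size basis, all of which say week 4. Nor is the choice between the two timings open to being made after the results are seen, because the plan already names week 4 as primary. The study also uses paper case report forms and standardised procedures that are not reproduced here, so the missing visit list does not show that the reading was unplanned.

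**Conclusion.** The concern does not call for a change. The design sentence and the week-4 endpoint differ by 2 weeks in group 2 and 8 weeks in group 3, but they are compatible, and the endpoint itself requires the week-4 reading in every group. This is missing detail that a competent team fills in the only way the stated primary analysis allows. A sentence making it explicit would be a harmless editorial clarification. It would alter no endpoint, test, sample size or conclusion, and power remains about 79% to 80% with 20 readings per group.

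This rests on two assumptions: that the measurement schedule follows the whole plan and not the design sentence alone, and that groups 2 and 3 attend in week 4 as their treatment schedules provide. Evidence that week-4 waist readings were in fact not taken in those groups would raise a serious question about conduct. Nothing in the documents says that they would be omitted.
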